2. HIPOTESIS:

Intermittent suction improves the diagnostic yield of pancreatic lesions compared to standard (continuous) suction. Up to our knowledge this method has not been yet evaluated.

3. STUDY DESIGN:

Interventional study with diagnostic purpose, longitudinal, prospective, unicentric, blinded for participant and anatomopathologist, in patients with solid pancreatic lesions with indication of cytological sampling by Endoscopic Ultrasound referred to the Endoscopy Unit of Hospital Universitario de la Princesa from January 2019 to December 2019.

Following clinical practice, an endoscopic ultrasound fine-needle aspiration (EUS-FNA) with a 25 gauge needle will be performed to each participant. The patients will be divided into two arms with a 1:1 ratio:

- a) Intermittent aspiration: Intervention arm. Endoscopic ultrasound will be done for the localization of the lesion and to localize the site of puncture. Prior to the puncture of the lesion the stylet is removed and a vacuum syringe is prepared with 10 cc of vacuum allowing the generation of continuous pressure inside and connected to the end of the needle. Once the lesion is punctured 15 movements in and out of the lesions will be made while the syringe is opened and closed on and off for a total of 3 times each pass. A total of 4 passes will be done in each lesion.
- b) Continuous/standard aspiration: Same procedure but once the lesion is punctured 15 movements in and out of the lesions will be made while the syringe remains opened.

Randomization will be done with the generation of a computer-generated random list using Epidat 4.0. software (SERGAS®, Santiago de Compostela, Spain).

The endoscopic ultrasound will be done with an Olympus linear echoendoscope (GF-UTC 260 Olympus® Tokyo, Japan) under Propofol sedation by an Anesthesiologist.

Each pass will be sent to the pathologist separately to evaluate their individual characteristics and to determine which one is diagnostic. A complete report will be done assessing:

- a) Cellularity
- b) Hematic contamination
- c) Presence of cell block and possibility of doing immunohistochemistry

4. OUTCOME MEASURES:

- a. Primary outcome measure: Increase in diagnostic yield of pancreatic solid lesions
- b. Secondary outcomes:
 - Sample Celularity: Number of malignant cluster of cells on each endoscopic pass
 - Blood contamination: Percentage of blood contamination of the slides
 - Number of passes to reach a positive cytological diagnosis

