5. ELEGIBILITY CRITERIA:

- a) Inclusion Criteria:
 - Pancreatic solid lesion
 - Patients over 18 years old
 - Suitable for endoscopy
- b) Exclusion Criteria:
 - Contraindication for endoscopy
 - Active anticoagulant therapy
 - Thrombocytopenia or coagulopathy in the absence of its correction prior to the procedure
 - Absence of informed consent
 - Pregnancy
 - Not accessible lesion for endoscopic ultrasound puncture

6. STATISTICAL ANALYSIS PLAN:

Data will be expressed as means and standard deviation for quantitative variables or frequencies and percentages for the categorical ones. Variables with non-normal distributions will be represented as means and percentage ranges.

Randomization will be done with a computer-generated random list in a 1: 1 ratio. The chi-square test will be used to compare qualitative variables. Correlation kappa values will be offered between both methods. In order to evaluate the differences in diagnostic yield, the sensitivity after the completion of each pass will be calculated by correlating the continuous values of confusion with the final cytology with the Spearman test. The number of optimal passes depending on the method will be calculated by maximizing that the following passes would not modify the additional diagnostic yield more than 10% over the accumulated one. On the other hand, the cellularity and blood contamination graduated in its three levels will be contrasted between both methods with an analysis of McNemar. All the variables that could potentially modify the diagnostic yield of both methods will be compared with univariate and later multivariate analysis by means of logistic regression analysis with the STATA application (v13.0, StataCorp, College Station, Texas, USA). The protocol will be approved by the Ethical Committee of the Hospital Universitario de la Princesa before the start of the study.

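### Cellularity and blood contamination are defined as a count and a percentage but tested as an undefined three-level grade, with a paired test across arms of different patients

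*Combined protocol and SAP*

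**What the plan says.** Section 4 (Outcome measures) lists two secondary outcomes on quantitative scales: "Sample Celularity: Number of malignant cluster of cells on each endoscopic pass" and "Blood contamination: Percentage of blood contamination of the slides". Neither definition mentions a grade.

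Section 3 (Study design) introduces the pathologist's report with "A complete report will be done assessing" and then names cellularity and haematic contamination, without a scale for either. The same section sets a parallel design, "The patients will be divided into two arms with a 1:1 ratio", and repeated sampling within each patient, "A total of 4 passes will be done in each lesion".

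Section 6 (Statistical analysis plan) gives the comparison: "the cellularity and blood contamination graduated in its three levels will be contrasted between both methods", by McNemar's test. It does not say what the three levels are. For quantitative variables it gives descriptive summaries only and names no test between arms. Its general test for qualitative variables is the chi-square.

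**The concern.** The endpoint in section 4 and the variable tested in section 6 are different quantities, and nothing in the documents connects them. Three things follow.

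- **Endpoint.** A reader cannot tell whether the reported result answers the stated question. Two of the three secondary outcomes are affected.
- **Information.** If a count and a percentage are recorded and then cut into three groups, part of what was measured is set aside. A test that ignores the order of the groups sets aside more. If the cuts are not written down, they can be chosen after the results are known.
- **Test.** McNemar's test compares paired binary responses. Here the arms contain different patients, so no pairs exist, and the variable has three levels. The four passes from one patient are correlated, and the named test does not deal with that either.

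Blinding of the pathologist protects the reading of slides. It does not fix the cut-points used at analysis.

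**Working it through.** **1. The sections side by side**

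| | Section 4 | Section 6 |
|---|---|---|
| Cellularity | count of malignant clusters, per pass | three levels, undefined |
| Blood contamination | percentage | three levels, undefined |
| Comparison of arms on the section 4 scale | – | none named |
| Test on the grade | – | McNemar (paired, binary) |

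The documents state no sample size, alpha, standard deviation or effect size for these outcomes, so there is no figure of the plan's own to reproduce. Everything below illustrates size under assumptions, with two-sided alpha 0.05 and one value per patient.

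**2. Information kept by three groups, normal shift**

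With cut-points c₁ and c₂ on the standard normal scale, the share of information kept is E = Σ [φ(cᵢ₋₁) − φ(cᵢ)]² / Pᵢ, where Pᵢ is the probability of group i and φ is zero at both extremes.

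For tertiles, c = ±0.431 and φ = 0.3636. Each outer group gives 0.3636² / (1/3) = 0.397 and the middle group gives 0, so E = 0.793. The sample size needed for the same power rises by 1/0.793 = 1.26.

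Set the uncut analysis at 80% power. The noncentrality is (1.960 + 0.842)² = 7.85, and after grouping 7.85 × 0.793 = 6.22. The ordered test then has power Φ(√6.22 − 1.960) = Φ(0.535) = 70%. An unordered chi-square on 2 df with noncentrality 6.22 has 60%.

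| Cuts (percentiles) | E | Ordered test | Chi-square, 2 df |
|---|---|---|---|
| 33 / 67 | 0.79 | 70% | 60% |
| 50 / 90 | 0.75 | 68% | 58% |
| 80 / 95 | 0.52 | 52% | 42% |

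Direct simulation at 30 per arm with a 0.75 SD shift agrees: about 79% for Mann-Whitney on raw values, 70% on ordered tertiles and 62% for the three-level chi-square.

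**3. Counts with structural zeros**

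Section 5 admits any pancreatic solid lesion, and section 1 says that such lesions may be non-neoplastic. A malignant-cluster count should be zero in those patients whatever the technique. Assumptions: 30 per arm, negative-binomial means 6 and 14, dispersion 1, levels 0 / 1-9 / 10 or more.

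| Structural zeros | Mann-Whitney on raw count | Three-level chi-square |
|---|---|---|
| none | 75% | 57% |
| 20% | 42% | 41% |
| 35% | 23% | 34% |

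A repeat run gave 40% against 40% at 20% zeros and 21% against 32% at 35%. The advantage of the raw count therefore depends on the case mix.

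**4. Open cut-points, no true effect**

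One pair fixed in advance gives about 5% false positives. Picking the smallest p-value from five pairs gives roughly 8-15% at 20-40 per arm, towards the lower end for an ordered test and the upper end for a chi-square. The best of three pairs gives about 10% and the best of six about 16% with a chi-square at 30 or 50 per arm.

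**The case against.** The strongest reply is that section 6 speaks of these variables as having three levels of their own. That reads naturally as a grade the pathologist assigns directly. If so, nothing measured is discarded and no cut-points are left for an analyst to choose; the fault is then in section 4's wording. This stands as a possible reading, and the documents do not settle it. It does not remove the point, because the scale is still unwritten, section 4 still states something else, and McNemar's test is still unsuitable.

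Three stronger readings are tempting and are not supported:

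- *The plan throws away measured data and so has less power.* This requires that the count and percentage are actually recorded and then grouped. Even then, the structural-zero results show that the loss is not general for cellularity.
- *The chi-square figure of about 62% is the power of the planned analysis.* It is not. The test named for these outcomes is McNemar's, which cannot be applied to the design as described. The chi-square is only what might replace it under section 6's general rule for qualitative variables.
- *The false-positive rate is inflated.* The plan leaves room for inflation. Nothing in the documents suggests that several sets of cuts would be tried and the best reported.

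It is also fair to say that these are secondary outcomes of a self-described pilot, and that with well-placed cuts and an ordered test the loss is modest.

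**Conclusion.** The point holds as a mismatch between stated and tested endpoints, combined with an undefined scale and a paired test in a parallel-group design. Those facts rest on the text alone and need no assumption.

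The size of the consequence is conditional. If the quantitative values are recorded and roughly normal, grouping costs around 9 points of power with an ordered test (79 − 70) and around 17 with an unordered one (79 − 62), at an assumed 30 per arm and a 0.75 SD shift. Badly placed cuts cost more. With many non-malignant lesions the cost for cellularity may be nil or reversed. The 8-15% false-positive rate is what selecting the best of five cut pairs would produce, not an expected rate.

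The primary outcome is not affected. The change is worth making because it is cheap and because, as written, neither secondary comparison can be carried out reproducibly.

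**What to change.** Before data review, state which measurement the pathologist records and bring sections 4 and 6 into line.

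- **If the count and percentage are recorded:** compare the arms on those scales with a method for independent groups that respects the four passes per patient, for example a Wilcoxon rank-sum test on each patient's mean. Also report cellularity among patients with a final diagnosis of malignancy, because the count is of malignant clusters. Keep any three-level table descriptive, with its cut-points written down in advance. A negative-binomial model would not suit the percentage, which is bounded.
- **If only a three-level grade is read:** redefine both outcomes in section 4 with that scale and the criteria for each level. Replace McNemar's test with an ordinal model, such as proportional odds, with clustering by patient.

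The cost is revised wording and slightly more analysis work. No new measurement is needed if the pathologist records what section 4 describes.
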